#### 10.1.5 Vital Signs

Vital signs evaluations will include blood pressure, pulse rate, and respiration rate. The investigator will record oral or rectal body temperature at baseline. Thereafter the subject will

record oral temperature twice daily in the study diary card.

Vital signs will be measured at Screening/Baseline, pre-dose, and at 15 minutes following the study drug injection on Day 1, then once daily on Days 3, 5, 9, and 14.

#### **10.1.6 Electrocardiogram Measurements**

A 12-lead electrocardiogram (ECG) will be obtained at Screening/Baseline. The principal investigator will be responsible for interpretation of the Screening ECG. This interpretation may be performed by the investigator or he/she may delegate this action to another physician and the investigator will acknowledge the interpretation. If this baseline ECG is interpreted as meeting the exclusionary criteria listed in section 8.1.2 the subject will not be enrolled in this study. If the ECG is interpreted as being abnormal but does not meet the exclusionary criteria, the subject may be enrolled unless other exclusion criteria apply. The principal investigator is responsible to ensure that such an enrolled subject be informed of the nature of the abnormal ECG and that any medically indicated repeat ECG examinations and/or referral of the subject for further evaluation is made either during subject's participation in the study or immediately after the subject's discharge from the study.

#### **10.1.7 Clinical Laboratories**

Clinical chemistry profiles will include a Chemistry 20 panel (includes sodium, potassium, chloride, total CO2 [bicarbonate], creatinine, glucose, urea nitrogen, albumin, total calcium, total magnesium, phosphorus, alkaline phosphatase, alanine aminotransferase (ALT), aspartate aminotransferase (AST), total bilirubin, direct bilirubin, lactate dehydrogenase [LDH], total protein, total creatine kinase, and uric acid).

Hematology will include complete blood count (CBC) with differential.

Urinalysis will include tests for protein, glucose, ketones, blood, urobilinogen, nitrite, pH, and specific gravity and microscopic evaluation for RBCs and WBCs. For any subject with a Day 3 positive test for urine protein of 2+ or higher, who had a Baseline/ Day 1 protein of <2+, a 24 hour urine collection for assessment of protein will be completed. All urinalysis tests will be completed by the central laboratory.

Clinical laboratory studies (clinical chemistries, hematology, and urinalysis) will be completed at Screening/Baseline, and on Days 3, 5 and 14.

#### **10.1.8 Urine Pregnancy Test**

Females of childbearing potential will be evaluated for pregnancy at Screening/Baseline and Day 14 using a urine pregnancy test.

#### **10.1.9 Serology for Influenza**

Paired blood samples for determination of antibody to influenza A and B (serology) will be obtained with the clinical laboratory tests at Screening/Enrollment and at Day 14. These specimens will be stored at the central laboratory and will be analyzed if needed to confirm the diagnosis of influenza.

#### **10.1.10 Samples for Virologic Laboratory Assessments**

An adequate specimen will be collected by swabbing the anterior nose (bilateral) and posterior pharynx for virologic laboratory assessments including culture for the isolation of influenza virus

and/or quantitative PCR assay at Screening/Baseline, and at Days 3, 5, and 9. Refer to the Laboratory Manual for instructions regarding the processing and shipment of these specimens.

#### **10.1.11 Subject Self Assessments**

Subject self assessments will be performed beginning pre-dose on Day 1 and recorded in the subject's Study Diary including the following:

- Oral temperature measurements with an electronic thermometer (provided by the Sponsor for the study) every 12 hours. With the exception of the baseline measurement, all temperature measurements will be obtained at least 4 hours after, or immediately before, administration of oral acetaminophen (paracetamol, provided) or other anti-pyretic medications. The times of each temperature determination will be recorded in the Study Diary. The baseline temperature will be recorded at the screening/Day 1 visit prior to dosing, regardless of whether the subject had recently taken an anti-pyretic.
- Assessment of seven influenza symptoms (cough, sore throat, nasal obstruction, myalgia [aches and pains], headache, feverishness, and fatigue) on a 4-point severity scale (0, absent; 1, mild; 2, moderate; 3, severe) twice daily, beginning pre-dose on Day 1 and through Day 9, then once daily through Day 14.
- Assessment of the subject's time lost from work or usual activities and productivity compared to normal using a 0-10 visual analogue scale once daily through Day 14.

The subject's diary card will be reviewed by study staff at each visit for completion of the record of all required items, with particular emphasis on alleviation of symptoms as well as relapse of symptoms. Relapse is defined as the recurrence of at least one respiratory symptom and one constitutional symptom (both greater than mild in severity) for 24 hours and the presence of fever (unless influenced by antipyretic use). Relapse can only occur after the subject has met the endpoint criteria for alleviation of symptoms. Study staff will not attempt to ask subjects to retrospectively complete missing diary card data for any scheduled assessments that have not been completed prior to the clinic visit. Study staff should, however, remind the subject to complete the diary card at all scheduled times.

#### **10.1.12 Concomitant Medications**

All concomitant medications used during this study, with the exception of those medications taken for symptomatic relief of influenza symptoms, which will be recorded by the subject in their diary card, must be documented on the Case Report Form (CRF).

#### **10.1.13 Adverse Events**

AEs will be assessed from the time of administration of study medication through the final study visit.

#### **10.1.14 Pharmacokinetic Exposure Samples**

All subjects will have two pharmacokinetic (PK) samples drawn to assess peramivir drug levels. The first PK sample will be drawn on day 1 between 30 and 60 minutes following study drug administration in all subjects. The second PK sample will be drawn at the day 3 visit in all subjects. The sample will be drawn at the same time as the blood draw is completed for clinical laboratory investigations. The 30-60 minute sample (treatment day 1) and the day 3 PK sample will be analyzed for plasma concentrations of peramivir (ng/mL) and evaluated in a population

exposure response analysis.

At selected sites a separate sub-study will also be conducted to collect additional PK samples for the purpose of conducting an exposure-response analysis. This sub-study will be conducted under a separate protocol, BCX1812-311PK. Data from these two PK samples in all subjects will be combined with data from the PK sub-study (BCX1812-311PK) to perform a population based exposure-response analysis. This analysis will be described as part of the sub-study analysis plan.

All PK samples will be processed at a central bioanalytical laboratory. Refer to the instructions provided regarding the processing and shipment of these PK samples.

## 10.2 Screening Period

### 10.2.1 Informed Consent

The nature and purpose of the study and the expectations of a participating subject will be described to potential study subjects, their questions will be answered, and the subjects will then be asked to sign an informed consent document. Study subjects will then undergo the screening evaluation as noted in Section 10.22

### 10.2.2 Screening/Baseline Evaluation and Enrollment

Screening/baseline evaluation may be conducted in the investigator's office or clinic, or in the subject's home, in which case all evaluations must be conducted by appropriately trained and qualified staff.

Clinical laboratory assessments performed at Screening are for the purpose of establishing a baseline. Subjects may be enrolled and receive treatment with study drug prior to receiving results of the laboratory assessments (with the exception of urine pregnancy test result, which must be known).

Eligible subjects will be enrolled and randomized to blinded study treatment. The randomization will be stratified by smoking status and RAT test for influenza A or B. The Investigator will prepare a request for blinded study drug assignment which includes the subject's screening number. The Investigator or designee at the clinical study center will contact the central randomization Interactive Voice System (IVRS call center). The IVRS call center will advise the study center of the investigational study drug kit number that is assigned to that subject at enrollment.

Subjects that are determined to be ineligible will be advised accordingly, and the reason for ineligibility will be discussed. If desired by the subject the reason for ineligibility may be provided and/or discussed with their health-care provider by the Investigator or designee.

Ineligible subjects who have been screened for the study will also be entered on the IVRS. For such subjects, the screening number assigned, subject's date of birth and a reason for ineligibility will be entered on to the IVRS. **All ineligible subjects must be entered onto the IVRS within 24 hours of screening**, to assist with surveillance analysis during the course of the study.

## 10.3 Treatment Period—Study Day 1

Day 1 represents the only day of study drug dosing. Study drug administration should occur as soon as possible following informed consent, screening and randomization. Therefore, it is

expected that the date of Screening/ Baseline and Day 1 will usually be the same date.

### 10.3.1 Pre-dose Evaluations-Study Day 1

Following an explanation of the Subject Self Assessment measures (Section 10.1.11), the subject shall complete the record of these assessments in their Study Diary prior to dosing. The subject will be counseled regarding the expectations for recording these assessments through Day 14.

Vital sign measurements (blood pressure, pulse rate, respiration rate, and oral temperature) and a 12 lead ECG will be obtained prior to dosing.

A nasopharyngeal swab for influenza culture/ PCR assay will be obtained prior to dosing.

### 10.3.2 Post-dose Evaluations-Study Day 1

The blinded study drug will be administered (hour 0) as bilateral intramuscular injections within a period of  $\leq 10$  minutes. The calendar date and 24-hour clock time of the first and second injections will be recorded. The gluteal site of injection and the syringe needle length are also to be recorded in the subjects CRF. Sites are instructed to follow procedures for intramuscular injection, with a recommended needle length appropriate to the physical characteristics of the subject, provided in the study drug administration manual.

The following evaluations will be performed post-dose on Study Day 1:

- Vital sign measurements (blood pressure, pulse rate, respiration rate, and oral temperature) 15 minutes following the second intramuscular injection of blinded study drug; record the exact 24-hour clock time of the vital sign measurements in the subjects CRF.
- Draw a PK sample between 30 and 60 minutes following the second intramuscular injection of blinded study drug; record the exact 24-hour clock time of the blood draw.
- Record any concomitant medications.
- Record any AEs.

## 10.4 Post-Treatment Assessment Period

### 10.4.1 Days 2, 3, 5, 9 and 14

Study evaluations will be performed on Days 2, 3, 5, 9 and 14 in accordance with the schedule of evaluations (Figure 1). Subjects with persistent moderate or severe influenza symptoms at day 14 will also complete a Day 21 visit, and if required a Day 28 visit.

Visits may be conducted in the investigator's office or clinic, or in the subject's home, in which case all evaluations must be conducted by appropriately trained and qualified staff.

Study staff will attempt to contact the subjects on Day 2 by telephone to confirm their compliance with completion of the Subject Self Assessments, to note any concomitant medications and adverse events. Any adverse events reported by the subject during this telephone contact will be recorded on the adverse event form and verified during the visit on day 3.

For any subject with a Day 3 positive test for urine protein of 2+ or higher, who had a Baseline/

Day 1 protein of  $<2+$ , a 24 hour urine collection for assessment of protein will be completed.

At each visit it is important that the subject's Study Diary record be reviewed for completion of daily Subject Self Assessments. The subjects should be counseled as necessary regarding self assessments and Study Diary record requirements. The subject's diary card will be reviewed by study staff for alleviation of symptoms as well as relapse of symptoms. Relapse is defined as the recurrence of at least one respiratory symptom and one constitutional symptom (both greater than mild in severity) for 24 hours and the presence of fever (unless influenced by antipyretic use). Relapse can only occur after the subject has met the endpoint criteria for alleviation of symptoms.

**Day 3:**

The second PK sample for all subjects will be obtained on Day 3 at the same time as the clinical laboratory blood specimen is obtained. The exact 24-hour clock time of the blood draw will be recorded in the subjects CRF.

**Day 14:**

If a subject has one or more persistent or recurrent symptoms of influenza (of the seven symptoms assessed) of either moderate or severe intensity at the Day 14 visit then the subject must be evaluated in further follow-up visits, at day 21 ( $\pm 3$  days), and if required at day 28 ( $\pm 3$  days) If a subject reports moderate or severe influenza symptoms then the investigator will record the intensity of each of the influenza symptoms on a visit specific CRF page at the day 21 and day 28 visits. After day 14 the subject will not record symptoms in a diary.

**Day 21 (if applicable):**

The day 21 visit is to be completed only if the subject reports symptoms of influenza of moderate or severe intensity at day 14. The investigator will make a clinical judgment as to the appropriate medical course of action for such subjects at the Day 21 visit and such action(s) will be recorded on the Day 21 CRF page. The investigator will recall the subject for a further study visit at day 28 ( $\pm 3$  days) if moderate or severe symptom(s) of influenza persist at Day 21.

**Day 28 (if applicable):**

The day 28 visit is to be completed only if the subject reports symptoms of influenza of moderate or severe intensity at day 21. The investigator will make a clinical judgment as to the appropriate medical course of action for such subjects at this visit and such action(s) will be recorded on the Day 28 CRF page. No further follow-up visits beyond day 28 are to be formally scheduled unless in the clinical judgment of the investigator further follow-up is required. The investigator will use his/her clinical judgment to manage the subject, referring the subject, if appropriate, for further medical care.

**10.4.2 Adverse Events Reported at Post-treatment Visits**

In this study, symptoms of influenza will be considered separately from adverse events reported during the post-treatment period. Accordingly, adverse events that have onset in the post-treatment period will be assessed and followed as specified in 11.2. Specifically, the investigator should attempt to follow all unresolved AEs and/or SAEs observed during the study until they are resolved, or are judged medically stable, or are otherwise medically explained.

**Figure 1 Study Measurements and Visit Schedule**

Assessments	Screening  (Baseline)	Treatment Period	Assessment Day				End of Study Early Withdrawal
		Day 1 	Day 2 	Day 3	Day 5 (±1 day)	Day 9 (±3 day)	Day 14 (±3 day) 
Informed Consent	X						
Rapid Antigen test for Influenza A and B	X						
Medical History/Physical Exam	X						
Influenza-related complications (IRC) checklist 	X			X	X	X	X
Inclusion/Exclusion	X						
Clinical Chemistries 	X			X	X		X
Hematology 	X			X	X		X
Exposure Pharmacokinetic Sample 		X		X 			
Serology (serum) Sample	X						X
Urinalysis 	X			X	X		X
Urine Pregnancy Test	X						X
Vital Signs 	X	X		X	X	X	X
ECG 	X						
Sample (nasopharyngeal swab) for Influenza Virus Culture/ PCR assay and for resistance studies		X		X	X	X	
Study Drug Administration		X					
Subject Diary Review 		X	X	X	X	X	X
Concomitant Medications	X	X	X	X	X	X	X
Adverse Events		X	X	X	X	X	X

Study Measurements and Visit Schedule Figure Legend on Next Page

## Study Measurements and Visit Schedule Figure Legend

-  It is expected that the date of Screening and Day 1 (date of administration of study drug) will be the same. Visits at Screening and on subsequent study days may occur in subject's home by the investigator (all visits) or appropriately trained study center staff (Day 3, 5, 9 visits).
-  Day 2 will be a telephone contact with the subject to ensure compliance with diary card completion, concomitant medication and adverse event review.
-  If an IRC is suspected then a targeted physical examination will be conducted to record the presence/absence of the IRC.
-  Clinical laboratory assessments performed at Screening are for the purpose of establishing a baseline. Subject may be enrolled and begin treatment with study drug prior to receiving results. A PK sample will be drawn 30-60 minutes following the second treatment administration injection. On Day 3 an extra tube will be included with the safety blood sample to collect the second PK sample for evaluation of peramivir concentrations.
-  Vital sign measures will include blood pressure, pulse rate and respiration rate. Vital signs will be recorded at Screening, pre-dose and at 15 min following the study drug administration on Day 1, then once on remaining days as stipulated. The investigator will record oral temperature at baseline. Thereafter the subject will report oral temperature measurements twice daily in the Study Diary
-  If the baseline ECG is interpreted by the conducting physician as meeting the exclusionary criteria listed in section 8.1.2 the subject will not be enrolled in this study. If the ECG is interpreted as being abnormal and does not meet the exclusionary criteria (e.g. acute ischemia, medically significant dysrhythmia) then this subject may be enrolled if the conditions highlighted in section 10.1.5 are met for the subject.
-  Subjects record symptom assessment in Study Diary, twice daily, beginning pre-dose on Day 1 through Day 9, then once daily through Day 14. Subjects record time lost from work or usual activities and rating of productivity compared to normal once daily through Day 14. Subjects record oral temperature twice daily throughout as well as all influenza related medications.
-  For any subject with unresolved moderate or severe intensity influenza symptoms a follow up assessment will be scheduled at Day 21 ( $\pm$  3 days) and Day 28 ( $\pm$  3 days) if required (See Section 10.4.1).
-  A PK sample will be drawn 30-60 minutes following the second treatment injection on Day 1, and on Day 3.
-  For any subject with a Day 3 positive test for urine protein of 2+ or higher, who had a Baseline/ Day 1 protein of <2+, a 24 hour urine collection for assessment of protein will be completed.

## 11 ADVERSE EVENT MANAGEMENT

### 11.1 Definitions

#### 11.1.1 Adverse Event

An AE is any untoward medical occurrence in a clinical study subject. No causal relationship with the study drug or with the clinical study itself is implied. An AE may be an unfavorable and unintended sign, symptom, syndrome, or illness that develops or worsens during the clinical study. Clinically relevant abnormal results of diagnostic procedures including abnormal laboratory findings (e.g., requiring unscheduled diagnostic procedures or treatment measures, or resulting in withdrawal from the study) are considered to be AEs.

AEs may be designated as “nonserious” or “serious” (see Section 11.1.2).

Surgical procedures are not AEs but may constitute therapeutic measures for conditions that require surgery. The condition for which the surgery is required is an AE, if it occurs or is detected during the study period. Planned surgical measures permitted by the clinical study protocol and the conditions(s) leading to these measures are not AEs, if the condition(s) was (were) known before the start of study treatment. In the latter case the condition should be reported as medical history.

Assessment of seven influenza symptoms (cough, sore throat, nasal obstruction, myalgia [aches and pains], headache, feverishness, and fatigue) will be documented in a subject’s study diary and analyzed as a measure of efficacy of the study treatment. These symptoms will not be reported as AEs unless the symptom(s) worsen to the extent that the outcome fulfils the definition of an SAE, which then must be recorded as such (see Section 11.1.2). Likewise, a RAT for influenza is required at screening in order to determine eligibility for the study, and therefore a positive RAT is not considered an AE.

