A majority of the first 40 subjects treated complained of acute pain immediately after injection at the ventrogluteal site and a number of these subjects reported that the pain was also associated with muscle cramping. Some subjects reported radiation of pain to the lower extremities. In most instances, these reactions abated after 15-30 minutes.

This protocol also evaluated the acute tolerability of doses of 450 mg and 600 mg of peramivir administered at the dorsogluteal site. Direct observations determined that the use of the dorsogluteal injection site resulted in an acute tolerability profile of the 600 mg dose of peramivir that was improved compared to that observed with ventrogluteal site injections. However, a number of these subjects also experienced acute pain and discomfort and some reported muscle cramping in the gluteal area which persisted for up to 30 minutes.

In summary, this study confirmed that the intramuscular injection of peramivir results in acute pain and discomfort after gluteal injection in the majority of subjects in whom total doses of up to 600mg are administered. In some subjects, the acute pain at the injection site may also be

associated with muscle cramping. Based on these findings, the dorsogluteal site will be utilized in future trials.

The safety data for i.m. peramivir administered as single doses ranging from 75 mg to 600mg at the dorsogluteal injection site in each of the 3 phase 1 studies conducted to date have been unremarkable. No serious adverse events were reported. The most commonly observed adverse events or laboratory abnormalities were injection site pain or discomfort, headache, and transient increases in muscle enzymes (CK). There have been several reports of signs and symptoms of self-limited vasovagal reactions following injections. No consistent differences in frequency of adverse events or laboratory toxicities were observed between the active and placebo treatment groups in the controlled phase 1 studies, with the exception that CK elevations appeared to be dose related in the peramivir treatment groups.

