#### 6.2.2 Secondary Endpoint(s)

Secondary safety, clinical, and virologic endpoints will include evaluations in each subject of:

Safety: Incidence of treatment-emergent adverse events and treatment-emergent changes in clinical laboratory tests.

Clinical: Time to resolution of fever; Incidence of influenza related complications.

Virologic: Quantitative change in influenza virus shedding, measured by viral titer assay (TCID50).

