## 12.7 Efficacy Analyses

### 12.7.1 Primary Efficacy Endpoint

The primary efficacy endpoint is the time to alleviation of symptoms of influenza in subjects diagnosed with influenza, defined as the time from injection of study drug to the start of the time period when a subject has Alleviation of Symptoms. A subject has Alleviation of Symptoms if all of the seven symptoms of influenza (nasal congestion, sore throat, cough, aches and pains, fatigue (tiredness), headache, feeling feverish) assessed on his/her subject diary are either absent or are present at no more than mild severity level and at this status for at least 21.5 hours (24 hours - 10%).

Descriptive statistics for the primary efficacy variable will be tabulated by treatment group. Alleviation of symptoms will be determined by assessment of symptoms as reported on each subject's diary card. Time to alleviation of symptoms will be summarized for each treatment group (300 mg peramivir and placebo). Treatment comparisons between the 300 mg peramivir group and placebo will be assessed using a Wilcoxon-Gehan statistic stratified by smoking status and positive PCR or viral culture for influenza A or B at screening for the ITTI and PPI populations. Subjects who do not experience alleviation of symptoms will be censored at the date of their last non-missing post-baseline assessment.

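### Version 4.0 section 11.1.1 keeps non-serious headache, fatigue and generalised myalgia out of AE reporting whatever their timing or cause, and no by-arm safety table named in the protocol picks them up

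*Combined protocol and SAP*

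**What the plan says.** All references are to protocol version 4.0 unless stated.

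- **AE rule (11.1.1).** A symptom that develops or worsens during the study is an AE. The section then lists the diary symptoms (cough, sore throat, nasal obstruction, myalgia, headache, feverishness, fatigue), assigns them to efficacy, and states: "These symptoms will not be reported as AEs unless the symptom(s) worsen to the extent that the outcome fulfils the definition of an SAE".
- **Post-treatment visits (10.4.2).** Here "symptoms of influenza will be considered separately from adverse events reported during the post-treatment period".
- **Endpoint (6.2.2).** The safety endpoint is "Incidence of treatment-emergent adverse events and treatment-emergent changes in clinical laboratory tests".
- **Phase 1 experience (5.5).** Headache is named with injection-site pain and CK rises among the most common findings. The same paragraph adds: "No consistent differences in frequency of adverse events or laboratory toxicities were observed between the active and placebo treatment groups", with dose-related CK rises as the exception.
- **Use of the diary (12.7.1).** "Time to alleviation of symptoms will be summarized for each treatment group (300 mg peramivir and placebo"), that is, as the seven-symptom composite.
- **Safety analyses (12.8).** These cover AEs, SAEs, vital signs, laboratory results, examination findings and concomitant medication. Diary scores are not mentioned.

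**The concern.** Safety and tolerability is the first secondary objective, and AE incidence is how the trial answers it. Keeping symptoms of the disease under study out of the AE count is reasonable while the patient has that disease. The rule, however, exempts by type of symptom and not by cause or time. It applies equally to a headache that was absent before the injection, one that begins after the influenza has been alleviated, and one the blinded investigator believes the injection caused.

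If such events are never AEs, similar AE tables in the two arms say nothing about them. A reader of the study report could take that silence as evidence of tolerability.

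**Working it through.** The plan gives no figure on this point and none is needed. The check follows a non-serious symptom through version 4.0.

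1. **Is it an AE?** The general definition in 11.1.1 would include it. The exemption then removes it by name, and the only way back is to meet the SAE definition. Neither timing nor attribution is mentioned. Section 10.4.2 speaks of influenza symptoms but does not say how a headache from another cause is to be told apart, or by whom.
2. **Is cause assessed?** Section 11.2.2 has the blinded investigator judge the relationship to study drug for each AE. A symptom that is not an AE gets no such judgement, and none can be recovered later.
3. **Does the diary show it by arm?** Scores run from pre-dose to Day 14 (10.1.11). Section 12.7.1 turns them into one composite time, tested in the ITTI and PPI populations. Section 12.10.3 subdivides by smoking status and influenza type. Section 12.8 does not use the diary. None of these compares arms symptom by symptom, and none of the composite analyses is for the safety population.
4. **Does relapse catch it?** Relapse needs a respiratory and a constitutional symptom, both above mild for 24 hours, together with fever unless antipyretics mask it (10.1.11). An isolated headache does not qualify, and section 12 plans no relapse analysis.
5. **A concrete case.** A subject has no headache before the dose, reaches Alleviation on Day 4, and has a moderate headache alone, without fever, on Day 6.

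| Where it could count | Result |
|---|---|
| Primary endpoint (12.7.1) | Alleviated on Day 4; unchanged |
| Relapse (10.1.11) | Not met |
| AE tables (11.1.1, 12.8) | Not an AE as the rule is written |
| Causality (11.2.2) | Not assessed |
| Data listings (section 12) | Score listed |

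6. **What is still captured.** Injection-site reactions are AEs (10.1.4), so local muscle pain is counted. Symptoms reaching SAE level enter the SAE summary (12.8). Oral temperature and time to resolution of fever are compared by arm (12.7.2). Where a diagnosis can be made, section 11.2 has the diagnosis recorded as the AE in place of its symptoms. What remains is non-serious headache, fatigue and generalised myalgia; the rule also covers the three respiratory symptoms.
7. **How strong is the phase 1 signal?** Section 5.5 supports headache as a commonly observed event and no more. The placebo arm it describes belongs to a study with six subjects per group. The two completed studies total 3 × 9 + 3 × 6 = 45 volunteers on peramivir, which matches the stated 45. Groups of that size neither establish nor exclude a moderate excess.

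**The case against.** **The exemption is deliberate and explained.** The symptoms are the efficacy measure, and counting them as AEs too would fill the AE tables with influenza. This stands as a reason for an exemption, but not for one without limits.

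**The text can be read more generously.** Sections 11.1.1 and 10.4.2 refer to influenza symptoms, so a headache after Alleviation might be thought to fall outside. That reading is possible, but the sentence in 11.1.1 points back to the seven listed symptoms whatever their cause. If sites may read it either way, AE counts will depend on the site, which also calls for a clarification.

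**Harm before Alleviation counts against the drug.** A drug-caused moderate headache delays the composite endpoint. This is true, but the delay cannot be separated from illness, and it does not apply after Alleviation.

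**The SAP may add the table.** Section 12.2 leaves detail to a SAP that is not in the supplied text. This stands: the finding is limited to tables named in the protocol. A SAP table could not, however, supply causality judgements that were never recorded.

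**Phase 2 lists no headache among its most frequent drug-related events (section 5.6, Table 4).** The documents do not say whether phase 2 used the same exemption, so this settles nothing either way.

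**Conclusion.** The point holds in a bounded form. Followed as written, version 4.0 leaves the AE endpoint unable to inform on non-serious headache, fatigue and generalised myalgia. This results from a stated rule, not from missing detail, and it should be changed.

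Four stronger readings are tempting, and the documents do not support them:

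- *That headache is a known reaction to peramivir.* Section 5.5 reports no consistent difference from placebo apart from CK.
- *That these symptoms can reach no planned output.* Serious cases are tabulated, temperature is compared by arm, all data are listed, and the SAP cannot be seen.
- *That drug-caused muscle pain is lost altogether.* Pain at the injection site is an AE; only generalised myalgia is affected.
- *That the loss can be put as a number.* No document gives a rate of drug-related headache, fatigue or myalgia in influenza patients, and influenza itself produces these symptoms at a high but unstated rate. No excess is therefore estimated here.

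Versions 1.0 and 2.0 planned a time-to-alleviation summary for individual symptoms. That is superseded text and was an efficacy summary, so the conclusion does not rest on it. The conclusion assumes that sites apply 11.1.1 literally and that the SAP does not already contain a by-symptom diary table for the safety population.

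**What to change.** 1. **Section 12.8 (and the SAP).** Add a descriptive by-arm table for the safety population, from the existing diary. For each of the seven symptoms, give the number of subjects (a) with the symptom absent pre-dose and present post-dose, (b) whose worst post-dose score exceeds the pre-dose score, and (c) with a new moderate or severe score after Alleviation. Add a note that counts before Alleviation also reflect the course of influenza and any antiviral effect, so that an effective drug could lower (a) and (b) and hide a harm. Row (c) is less exposed to this.
2. **Sections 11.1.1 and 10.4.2.** Limit the exemption to symptoms attributed to the current influenza illness. A symptom that the blinded investigator judges related to study drug, or that first appears after Alleviation without relapse, is recorded as an AE and so receives the causality assessment in 11.2.2.

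**Cost.** Item 1 needs no new data and can be added at any time before unblinding; if the SAP already has the table, it is met. Item 2 works only for events recorded after the change. It brings some extra AE pages, subjective attribution in patients who are still ill, and slightly less favourable AE counts. Neither item alters the primary endpoint, the dosing or the visit schedule.
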